## **F2. Baseline differences**

Chi-squares and t-tests will be used to assess the effectiveness of our randomization procedures, (i.e., compare CLASP to SAFE on demographic variables, diagnosis, suicide history and characteristics of previous attempt, and presence and severity of other suicide risk factors).

## **F3. Treatment Outcome (Primary, Secondary, and Tertiary Hypotheses)**

We will employ a similar analytic approach for all treatment outcomes. The primary focus of our treatment outcome analyses will be to identify differences between CLASP and SAFE for our major outcome measures (i.e. number of suicide attempts, severity and chronicity of suicidal ideation, rate of psychiatric hospitalization, psychiatric symptoms, psychosocial functioning and treatment engagement). The primary outcome analyses of the efficacy of the CLASP condition relative to the SAFE condition will assess subsequent suicidal behavior. Secondary analyses will focus on potential differences in psychiatric re-hospitalization, and suicidal ideation. Tertiary analyses will explore treatment engagement and potential differences in areas of psychiatric symptoms and psychosocial functioning.

### **F3.1 Operationalization of Outcomes.**

#### 1) Primary Outcome

- a. *Suicide Attempts*. The number of patients who make a subsequent suicide attempt and total number of attempts will be assessed using 12 month data collected from all possible sources, including follow-up assessments (C-SSRS), b) hospital chart reviews, c) significant other reports, and d) community clinician reports.

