## **D2. Participants**

Participants for this study will consist of 200 inpatients from the Providence Veterans Affairs Medical Center and 100 identified significant others. **Inclusion criteria** for the Veteran participant will include: 1) suicide attempt or suicidal ideation with any methods, plan, and/or intent to make a suicide attempt within 1 week of hospitalization as indicated on the hospital chart and/or confirmed by administration of the C-SSRS [48]; 2) age greater than 18 years, 3) have a telephone, and 4) ability to speak, read, and/or understand spoken English sufficiently well to complete the procedures of the study. **Exclusion criteria** will include: 1) diagnosis of primary psychotic disorder based on chart review (e.g. Schizophrenia or Schizoaffective disorder), 2) diagnosis of borderline personality disorder (based on screening with MSI-BPD [49], followed by BPD section of SCID-II if MSI-BPD is positive), or 3) cognitive impairment which would interfere with adequate participation in the project (MMSE [50] < 20).

We will also enroll patients' significant others/family members for those assigned to CLASP intervention; n=100). Significant others will only be recruited to serve as a primary support person for the intervention. Their participation will be limited to 1 joint-family session with the Veteran participant and a series of phone sessions. All sessions will be focused on the Veteran participant. Significant others will not be asked to complete any questionnaires or interviews and no personal information other than name and phone number will be collected. **Inclusion criteria** for significant others will include: 1) age greater than 18 years, 2) have a telephone, & 3) ability to speak, read, and/or understand spoken English sufficiently well to complete the procedures of the study.

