### **D2.1 Identification of potential participants.**

- 1) Chart review: Research staff will use CPRS to identify at-risk Veterans using the inclusion and exclusion criteria listed above. Potentially eligible participants will be approached on either the inpatient psychiatric unit or medical unit by a member of our research team and will be given information about the study. If they are interested in participating they will complete informed consent prior to any assessment or study participation. All informed consent of Veterans will occur in person while the participant is on the inpatient unit.
- 2) Physician and/or therapist referrals: Study personnel will provide study brochures and flyers to providers and staff on the inpatient unit. A member of the research staff will stop by the unit on a weekly basis to talk to any identified patients or answer questions about the study.
- 3) Referrals from the Providence VAMC Suicide Prevention Coordinator: [name] will provide study brochures and flyers to the local Suicide Prevention Coordinator and potential participants will be encouraged to contact the study if interested in participating.

**D2.2 Recruitment of Veteran patients.** There are several methods of recruitment that will be employed.

- 1) A recruitment brochure has been designed to reach eligible Veterans. Included on this brochure is contact information for the principal investigator for a screening. Brochures are distributed to inpatient physicians, the Suicide Prevention Coordinator and staff on the inpatient unit.
- 2) Presentations are made by the principal investigator to Veteran, inpatient staff, and the Suicide Prevention Coordinator to provide an opportunity for referring agencies, or potential participants, to inquire further.
- 3) VA clinicians who have patients interested in the study can obtain a release of information for our study to contact the patient directly.

**D2.3 Recruitment of family members or significant others.** Veterans randomized to the intervention arm of the study will be asked to identify a significant other to participate in the intervention with them. Significant others can be family members, partners, close friends, or other

identified support persons. In all cases, the Veteran patient will be asked to identify a significant other to participate with them prior to any contact between significant other and research staff. Several methods of recruitment for significant others will be used.

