## D6. Study Procedures

Research staff will approach potentially eligible participants during inpatient hospitalization in either the medical unit or the psychiatric inpatient unit. If interested, informed consent will be obtained and research staff will coordinate with the Veteran patient and inpatient staff in order to conduct the baseline assessment. Eligible patients will be enrolled in the study.

After enrollment patients will be randomized to 1) Safety Assessment and Follow-up Evaluation (SAFE) or 2) CLASP for a six month period. We will use the urn randomization strategy described by Wei [63] and Stout [64] to help insure balance among treatment groups. Urn randomization is a stratified randomization technique, which randomly assigns patients of a given subgroup to treatment conditions, but systematically biases the randomization in favor of balance among the treatment conditions on the stratification variables. For this study, we will be balancing the treatment groups on the following stratification variables: 1) gender of participant (male or female); 2) number of previous suicide attempts (zero, one, many) and 3) recent intake for suicidal ideation vs suicide attempt. We have successfully used the urn randomization procedure in several previous treatment outcome studies [65, 66] and have acquired an electronic file that contains the algorithm for urn randomization

[67]. This file also will provide the ability to monitor effectiveness of our stratification and randomization procedures. Patients assigned to the CLASP intervention will be asked to identify and reach out to a significant other to participate with them. For those in the CLASP intervention, research staff will attempt to complete 3 in-person individual sessions and 1 in-person joint session while the patient is hospitalized. In the event that the patient is discharged prior to the completion of in-person sessions, those sessions will be scheduled in the 1-2 weeks after the patient has left the hospital and will be conducted in assessment rooms in the Research building.

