  - a. *Individual In-Person Meetings.* Meeting 1 focuses on rapport building. The advisor inquires about the events leading to hospitalization, emphasizing the links between identified risk factors and suicidality. The advisor assesses current risk behaviors. The advisor also provides brief psychoeducation about suicidality. Next, values clarification is introduced based on ACT to motivate change and instill hopefulness. In Meeting 2, the advisor reviews and finishes the values clarification discussion as needed and helps the patient define specific behavioral goals that are consistent with the values. The advisor helps the patient define a list of short-term, values-consistent goals. The majority of Meeting 3 is spent formulating an individualized "Life Plan." The Life Plan document contains various questions for the patient and advisor to discuss and record responses, such as "What is my plan of action for keeping safe?" and "How will I recognize my early warning signs so I can take action sooner?" The advisor and patient also formulate a specific safety plan to address any suicidality following hospitalization. Potential barriers to attending scheduled sessions within the VA post-discharge are discussed and the role of the Suicide Prevention Coordinator is discussed.
  - b. *SO In-Person Meeting.* Meeting 4 includes the advisor, patient, and a significant other (SO) following the FITT format. The advisor reviews the psycho-educational information with the patient and SO. The advisor asks the SO to discuss his/her perspective on the patient's recent hospitalization. The majority of the session is spent reviewing the patient's Life Plan. The advisor facilitates a discussion between the SO and patient about the role the SO can play in the treatment plan to support the patient's goals. If severe patient-SO conflict is identified referrals for family therapy are provided.
  - c. *Telephone contacts.* Following the in-person meetings, the advisor conducts Telephone Contacts 1-11 with the patient and their SO individually. To further personalize the intervention and decrease potential treatment burden, each session is 15-30 min in length based on the number and severity of clinical issues identified. Sessions are conducted on a schedule of decreasing frequency for a target of 11 sessions over 6 months. At the start of

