each contact, the advisor conducts a quick assessment of risk factors (e.g., psychiatric severity, suicidality, treatment adherence, social support) since last contact. If suicidality is identified, this is discussed first and a safety plan is developed. The advisor facilitates problem-solving and communication between the patient and SO. The advisor discusses problems in terms of values strategies and in reference to the previously developed Life Plan document. If a problem develops that cannot be solved in this manner, the advisor may obtain permission to contact the patient's primary treatment provider directly or temporarily increase the frequency of the phone contacts during times of crisis. The SO phone contact proceeds in a similar manner. The VA Suicide Prevention Coordinator will be informed of any increase in risk.

2) *Description of Control Condition.* The choice of a comparison or control condition for suicide prevention research has been the subject of much debate [68]. For a variety of ethical, pragmatic and research concerns, the most commonly used control group has been some variant of "Treatment as Usual (TAU)." Although use of TAU as a control group has some limitations [69], it also has many advantages [70]. Since the CLASP intervention is designed to be an "adjunctive" intervention, the use of a variant of TAU seems particularly appropriate. Empirically, this decision allows for the evaluation of CLASP as a true adjunctive intervention, as we will be able to evaluate the additive benefits of CLASP over and above TAU. This design also reflects the manner in which CLASP would likely be implemented in the VA setting (i.e., to Veterans already identified as being at risk for suicide). However, given the high risk nature of this proposed sample, in order to provide an ethically appropriate "comparison" condition, we have developed and piloted a comparison condition which enhances "treatment as usual" with additional assessment and clinician feedback.

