Veteran patients randomized to the CLASP intervention will be asked to identify a significant other to participate with them. One goal of the study is to increase communication and social support between patients and their family members. Patients and their significant others will be encouraged to share information from the phone calls and patients will be told to share specific information such as new difficulties or safety issues with their participating significant others. Furthermore, Veteran patients will be told that the significant other phone calls are intended to a) increase social support, b) gain additional information on how the Veteran is currently functioning from the perspective of the significant other, and c) provide a backup in the event that the patient is feeling unsafe and needs support engaging in care. No questionnaire or interview data will be collected from any significant other and limits of confidentiality will be outlined in the consent forms.

- 3) *Distress as a result of completing the assessment procedures:* All assessments (including clinical assessments such as the SCID and C-SSRS, self-report questionnaire packet & treatment evaluation interview) will be administered by research personnel who are trained in the assessment battery and who have human subjects certification. [name], a licensed clinician who will be available to speak with the participant in the event of any adverse event, will supervise all assessments and interviews. Participants who are ineligible for the study will be provided with a list of mental health referrals specific to their location. Individuals may also be referred to their current providers or emergency services as appropriate. While we do not anticipate that participants experience significant distress while completing the assessment measures, we will ensure that a licensed clinician is available during all assessments should participants experience any distress. Should any safety issues be raised during the assessment we will follow standard protocol (see section on safety monitoring and managing adverse events).

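### The primary outcome counts significant-other reports, but significant others are contacted only in CLASP, so attempts known only by that route can be counted in one arm and not the other

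*Combined protocol and SAP*

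**What the plan says.** F3.1 (Primary Outcome) defines both the number of patients with an attempt and the total number of attempts over 12 months, with the information to be "collected from all possible sources, including follow-up assessments (C-SSRS), b) hospital chart reviews, c) significant other reports, and d) community clinician reports". The list is open-ended.

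On who has a significant other in the study:
- D2.3: "Veterans randomized to the intervention arm of the study will be asked to identify a significant other to participate in the intervention with them".
- D6: "Patients assigned to the CLASP intervention will be asked to identify and reach out to a significant other to participate with them".
- D2 plans 100 significant others, all for patients assigned to CLASP, and adds: "Significant others will not be asked to complete any questionnaires or interviews". G2.2 repeats that no such data are collected from them.

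On contact during the intervention, D6.1 says "the advisor conducts Telephone Contacts 1-11 with the patient and their SO individually", aiming for 11 calls in 6 months. Every call opens with a check in which "the advisor conducts a quick assessment of risk factors (e.g., psychiatric severity, suicidality, treatment adherence, social support) since last contact". G2.2 gives one purpose of the significant-other calls as to "gain additional information on how the Veteran is currently functioning from the perspective of the significant other".

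Some ascertainment is common to both arms. D5 has follow-up assessments at 3, 6, 9 and 12 months done by evaluators blind to condition. Its table lists C-SSRS, LIFE, and review of hospital records and death registries at follow-up.

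**The concern.** Attempts should be found with the same probability in both arms. Here two routes exist in CLASP only: what a significant other tells the advisor, and what the patient tells the advisor. The first is named in the outcome definition; the second is not excluded by it. Nothing limits the primary count to sources shared by the arms, and nothing says attempts are classified blind to arm. The blinding in D5 protects the interviews, which are one source among several.

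At stake is the primary comparison. Extra detection in CLASP raises the observed CLASP rate, shrinks the observed effect and costs some power. There is also an internal inconsistency: F3.1 relies on reports from people whom D2 and G2.2 exclude from formal data collection.

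**Working it through.** **Routes by arm**

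| Source of attempt data | CLASP | SAFE |
|---|---|---|
| Blinded interviews, 3 to 12 months (D5) | yes | yes |
| Hospital records, death registries (D5) | yes | yes |
| Significant other, via advisor (D6.1, G2.2) | yes, for 6 months | no route described |
| Patient, via advisor (D6.1) | yes, for 6 months | none |
| Clinician reports to the study (F3.1) | procedure not stated | procedure not stated |

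**Plan's own figure.** F5 gives power .82 from Fisher's exact test, one-tailed, alpha .05, N = 200, with pilot rates 3/39 = 7.7% and 10/47 = 21.3%. With 100 per arm assumed, the exact calculation over both binomials gives .833, close to the stated value. The risk ratio is 7.7/21.3 = 0.36.

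**Illustration 1: assumed detection rates.** Observed rate = pilot rate × detection. The last column is the rate of rejecting in favour of CLASP when both true rates are 21.3%.

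| Detection, CLASP/SAFE | Power | Risk ratio | Rejection, no true effect |
|---|---|---|---|
| 90%/90% | .786 | 0.36 | .035 |
| 95%/90% | .754 | 0.38 | .023 |
| 80%/80% | .729 | 0.36 | .034 |
| 90%/80% | .653 | 0.41 | .014 |

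**Illustration 2: recovery limited by contact.** CLASP detection = (1 − m) + m × r × c × s. Here m is the share missed by common sources, s the share of attempts in months 0 to 6, and r the share recovered when there is contact; all three are assumed. Coverage c uses C1.2 as a proxy: 29 of 39 pilot CLASP patients engaged (39 − 10) and about 75% of contacts were completed, so c = 29/39 × 0.75 = .558. SAFE detection = 1 − m.
- Mild (m = .10, r = .5, s = .5): CLASP detection .90 + .10 × .5 × .558 × .5 = .914. Power goes from .786 to .777. Extra CLASP attempters per 100: 7.7 × .014 = 0.1.
- Strong (m = .20, r = 1, s = .75): .80 + .20 × 1 × .558 × .75 = .884. Power goes from .729 to .666. Extra attempters: 7.7 × .084 = 0.6. Risk ratio 0.40.
- With no true effect, rejection in favour of CLASP is .031 (mild) and .016 (strong).

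**Illustration 3: pilot rates taken as already containing the extra events.** Suppose 0.5 (or 1) of the 7.7 CLASP attempters per 100 were known only through a significant other or advisor. A common-source count would then give (7.7 − 0.5)/21.3 = 0.34, or (7.7 − 1)/21.3 = 0.31. Power would be .865 or .892, against .833.

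**The case against.** - **A reader might infer that the trial falls short of its stated power. The documents do not support that.** C1 says the pilot used identical procedures, and C1.3 lists significant-other reports among its sources. If the asymmetry operated there, the rates behind .82 already contain it, and illustrations 1 and 2 discount them a second time. Only illustration 3 avoids this, and it shows a possible gain rather than a deficit. This objection stands.
- **A reader might also infer that the whole outcome is biased against CLASP.** That holds only for the two advisor routes. D6.1 describes releases and reports to clinicians under SAFE, while G2.2 describes monitoring and study notes more generally. Neither says whether incoming clinician reports are requested identically by arm, so the net direction is open.
- **The source may be nearly empty.** Significant others are recruited only as support persons, patients without one may still take part (G2.2), and calls cover 6 of the 12 months. G1.2 describes the analysis database as participants' own responses. Pilot non-engagers could not be reached after discharge, so patients missed by interviews may also be missed by advisors, and illustration 2 may overstate recovery. This bears on size. It does not remove the source from F3.1.
- **Counting every known attempt is defensible for this endpoint, and dropping CLASP events favours the experimental arm.** This is a fair point. It is why an all-sources analysis must accompany the common-source count.

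**Conclusion.** Followed as written, the plan makes ascertainment of the primary outcome depend on arm. For the significant-other and advisor routes the direction is toward no effect, and the rejection rates under no true effect fall rather than rise, so no false efficacy claim follows.

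The size cannot be read from the documents. Under the assumptions shown, the contact-limited range is 0.1 to 0.6 extra CLASP attempters per 100 and about 1 to 6 points of power (.786 − .777 = .009; .729 − .666 = .063). It may be very small, given blinded interviews and record review in both arms. These figures rest on assumed detection rates and 100 patients per arm. The asymmetry itself rests on the text. Priority is modest: the point touches the primary endpoint and is cheap to correct.

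**What to change.** 1. In F3.1, define the primary count from sources collected by the same procedure and schedule in both arms: blinded C-SSRS and LIFE interviews, hospital record review and death registries. Include clinician reports only if they are requested identically in both arms, and say so.
2. Record the source of every event, and flag chart entries that originate from a study note.
3. Report an all-sources sensitivity analysis that adds events known only through a significant other or advisor, so that no known attempt is left out.
4. Reconcile F3.1 with the statements in D2 and G2.2 that significant others supply no questionnaire or interview data.
5. If attempts are classified blind to arm, use event summaries with arm, source and study-note content removed. Unredacted charts or source labels could unblind raters who still conduct follow-up interviews.

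**Cost.** A short edit, one field on the event form and, if step 5 is adopted, summaries for about 29 expected attempters (7.7 + 21.3 at pilot rates, 100 per arm).

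**Downside.** A few true CLASP attempts leave the primary count, which lowers the CLASP rate. Some advisor-known events may still reach the records through study notes in CPRS (G2.2), or because "The VA Suicide Prevention Coordinator will be informed of any increase in risk" (D6.1). The flag shows study-note entries but does not remove them.

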#### 2) Secondary Outcomes

- a. *Re-Hospitalizations due to Suicide Risk*. Although re-hospitalization may be function of multiple factors, including actual level of suicidal risk, it can provide a rough measure of subsequent risk, and is an important health services outcome. For these reasons, we will use the Treatment History Interview as well as hospital records and clinicians' reports to track # of subsequent psychiatric hospitalizations and reasons for these admissions
- b. *Suicidal Ideation*. Significant suicidal ideation will be operationalized through measures of severity and chronicity of suicidal ideation generated by the Longitudinal Interval Follow-Up Evaluation (LIFE). Using the methodology of the LIFE, at each assessment point, we will ask participants to rate their level of suicidal ideation in the preceding 13 weeks on a 6-point psychiatric status rating (PSR) scale. This methodology, which yields weekly scores, allows us to examine both the occurrence of significant suicidal ideation throughout the course of the study as well as the chronicity of suicidal ideation as an outcome, which we believe is a clinically relevant distinction from pre-post change in level of suicidal ideation. These methods have been successfully implemented in two NIMH-funded studies at Brown [75][76] and [name] is currently utilizing this methodology in a treatment development study of suicidal adolescents [77]. We will also assess severity of suicidal ideation more traditionally using the Suicidal Intensity subscale from the C-SSRS.

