**A2. Secondary Hypotheses**

When compared to patients receiving SAFE, patients assigned to the CLASP intervention will have: a) fewer re-hospitalizations due to suicide risk, and b) lower severity and chronicity of suicidal ideation.

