**D. Research Design and Methods.**

## **D1. Overview**

Two hundred Veterans admitted to the Providence VAMC psychiatric inpatient unit or medical unit due to suicide attempt or suicidal ideation with any methods, plan, and/or intent to make an attempt will be recruited and randomly assigned to receive treatment as usual and either: a) SAFE or b) CLASP. The active interventions will begin during hospitalization and continue for 6 months post-discharge. After the intervention's end, patients will be followed for follow-up assessments for an additional 6 months (12 months post-discharge).

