#### **F4. Change Trajectory**

We will use latent growth curve modeling to explore the trajectory of change in our outcome measures specified above. These models will initially be specified as parallel growth processes (i.e. simultaneous modeling of suicide attempts, suicidal ideation, and psychiatric hospitalization) to account for shared variance, but will be tested individually if a parallel growth model cannot be fit. Using data collected across our 5 assessments, we will estimate intercept (i.e. mean) and slope (i.e. linear rate of increase/decrease) for each of these latent suicide risk constructs. As we expect participants will show clinical improvements at the end of the CLASP protocol, with some participants deteriorating in the follow-up (with a similar, but more pronounced intensity of response for SAFE participants) we will also investigate quadratic slope (i.e. curvilinear change trajectory). To account for time, we will fix our initial two time points, and allow MPlus to estimate the remaining time parameters. We first fit unconditional models to identify the optimal change trajectory for each outcome.

Once the optimal growth trajectory has been identified, we then fit conditional growth models in which growth parameters (i.e. intercept, slope, quadratic slope) are regressed on selected predictor variables (i.e. treatment assignment, covariates, and/or moderator variables of interest). We chose this analytic approach because it permits us to both take advantage of the repeated suicide assessments and to model variations associated with the implementation and cessation of treatment. We will be able to add additional predictors to the model iteratively, to explore the unique and overlapping predictive utility of each measure. However, we recognize that as with any latent variable modeling approach, we may experience difficulty with model fit. In the event that we are unable to fit a model to the data, we will either modify our model (i.e. exclusion of a risk variable, inclusion of covariance between predictors, change in time parameterization, etc.) or employ a simplified multilevel modeling approach (i.e. HLM) or multiple linear regressions.

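### The A2a re-hospitalization endpoint is named in two different ways, and its tracking rule, read literally, leaves out medical-unit admissions for a suicide attempt

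*Combined protocol and SAP*

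**What the plan says.** Section A2 states the hypothesis as "fewer re-hospitalizations due to suicide risk". In F3.1 the outcome carries the heading "Re-Hospitalizations due to Suicide Risk". The text beneath it says "we will use the Treatment History Interview as well as hospital records and clinicians' reports", and the purpose is "to track # of subsequent psychiatric hospitalizations and reasons for these admissions". F3.2 includes suicide-related re-hospitalization among the outcomes for which a CLASP effect will be estimated.

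F3 and F4 use other terms. F3 puts "rate of psychiatric hospitalization, psychiatric symptoms, psychosocial functioning and treatment engagement" in its list of major outcomes and adds: "Secondary analyses will focus on potential differences in psychiatric re-hospitalization, and suicidal ideation". F4 plans "simultaneous modeling of suicide attempts, suicidal ideation, and psychiatric hospitalization".

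On entry, D1 recruits veterans admitted to the "psychiatric inpatient unit or medical unit due to suicide attempt" or for suicidal ideation. D2.1 and D6 also name the medical unit as a place of recruitment.

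The pilot outcome in C1.3 was readmission because of an attempt or risk. F5 quotes its counts, 8 of 39 for CLASP and 17 of 47 for control.

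**The concern.** Two analysts could follow this plan faithfully and test A2a on different events. One who starts from A2 and F3.2 would count admissions due to suicide risk. One who starts from F3 or F4 would count psychiatric admissions, including any for another reason. Nothing in the plan says which prevails, so the choice could be made after the data are seen.

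The tracking rule raises a separate problem, on the side of omission. Reasons are to be recorded for psychiatric hospitalizations. A veteran who overdoses, is treated on a medical unit and is discharged from there has been readmitted because of an attempt, which A2a covers. As written, that admission is neither counted nor given a reason. The recorded reasons can separate suicide-related from other psychiatric admissions, but they cannot bring back an admission that was never listed.

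No section says how a recorded reason makes an admission suicide-related, who decides, or whether that person knows the arm.

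**Working it through.** **1. The sections side by side**

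| Section | Event named | Suicide qualifier | Medical-unit admission for an attempt |
|---|---|---|---|
| A2 | re-hospitalization | yes | covered by the wording |
| C1.3 (pilot) | re-hospitalization | yes | covered by the wording |
| F3 | psychiatric (re-)hospitalization | no | not covered |
| F3.1 heading | re-hospitalization | yes | covered by the wording |
| F3.1 text | psychiatric hospitalizations, with reasons | only through the reasons | not covered |
| F3.2 | re-hospitalization | yes | covered by the wording |
| F4 | psychiatric hospitalization | no | not covered |
| F5 (pilot counts) | both terms, same figures | yes | not stated |

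The event sets differ in two directions. F3 and F4 can add psychiatric admissions for other reasons. F3, F4 and the F3.1 text can drop medical-unit admissions for an attempt.

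**2. The plan's own figure**

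F5 states power .82 for suicide attempts: Fisher's exact test, one-tailed, α = .05, N = 200. I take 100 per arm, from two arms and the 100 significant others planned for CLASP. Exact power is the sum, over all pairs of counts (x₁, x₂), of Bin(x₁; 100, p₁) × Bin(x₂; 100, p₂), restricted to pairs whose one-tailed Fisher p-value is at most .05.

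- p₁ = 3/39, p₂ = 10/47: power .833.
- Rounded to 8% and 21%: power .799.

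The stated .82 lies between these, so it reproduces. It concerns attempts and is not affected by this point. F5 gives no two-proportion power for re-hospitalization.

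**3. Illustration for re-hospitalization**

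Pilot rates: 8/39 = .205 and 17/47 = .362, a difference of .157. The same calculation gives power .753.

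*Unrelated psychiatric admissions counted.* Let u be the share of the remaining patients in each arm who have one. Then p′ = p + (1 − p)u, and the difference shrinks by the factor (1 − u). For u = .10, CLASP is .205 + .795 × .10 = .285 and SAFE is .362 + .638 × .10 = .426.

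*Medical-unit admissions missed.* Let m be the share of patients with a suicide-related readmission whose only such admission was to a medical unit. Then p′ = p(1 − m). For m = .10, CLASP is .205 × .90 = .185 and SAFE is .362 × .90 = .326.

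| Assumption | CLASP | SAFE | Difference | Power |
|---|---|---|---|---|
| none | .205 | .362 | .157 | .753 |
| u = .05 | .245 | .394 | .149 | .684 |
| u = .10 | .285 | .426 | .141 | .612 |
| u = .20 | .364 | .489 | .125 | .503 |
| m = .10 | .185 | .326 | .141 | .694 |
| m = .20 | .164 | .289 | .125 | .629 |

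The values of u and m are assumptions; the documents give neither. The pilot rates cover six months and the trial twelve. The plan does not name a Fisher test for this outcome; F3.2 points to GEE-type analyses. The table shows the direction of each departure and a plausible order of size, no more.

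**The case against.** The best defence is that F3 and F4 use shorthand. F5 calls the pilot outcome psychiatric re-hospitalization and, in the same sentence, readmission for suicide risk, with the same counts. F4 refers back to the outcomes already specified and treats its variables as suicide-risk constructs. F3.2, which sets out the outcome analyses, keeps the suicide qualifier. F3.1 records reasons under a heading limited to suicide risk, so the suicide-related psychiatric admissions can be derived. All of this stands. It makes the suicide-specific reading the likelier intention, but it does not make F3 and F4 say so.

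On medical units, the defence is that no section expressly excludes them and that hospital records are a named source. That is fair, but the tracked quantity is psychiatric hospitalizations, and no section extends it.

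A reader might infer four stronger things that the documents do not support:

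- *That only all-reason psychiatric admission will be analysed.* F3.2 contradicts this.
- *That medically serious attempts are lost to the trial.* The primary outcome in F3.1 draws on the C-SSRS, hospital chart review, significant-other reports and community clinician reports, so the attempt should be captured there.
- *That CLASP would raise unrelated admissions because it promotes engagement.* F3.1 defines engagement as seeing a mental health professional in the month before an assessment, which says nothing about inpatient admission.
- *That a move from medical to psychiatric unit within the index stay would count.* The outcome concerns subsequent re-hospitalization, and follow-up is timed from discharge, so on an ordinary reading it would not.

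**Conclusion.** The point holds as an inconsistency in one secondary endpoint together with a gap in its tracking rule. A2, the F3.1 heading and F3.2 specify suicide-related re-hospitalization; F3 and F4 name a wider psychiatric variable. The F3.1 text, followed literally, leaves out medical-unit admissions for an attempt, which A2a covers and D1 accepts for entry. The second part rests on giving the word psychiatric its plain meaning.

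The size cannot be fixed from the documents. Under equal shares in both arms, either departure narrows the difference and lowers power from .753 at the pilot rates, but the amounts shown depend on assumed shares and on a test not planned for this outcome. They do not show that the A2a analysis will be underpowered by any particular amount. The primary hypothesis and its stated power are unaffected.

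**What to change.** Use one definition in F3, F3.1, F3.2 and F4, for example: any inpatient admission after index discharge, to a psychiatric or medical unit, whose recorded reason is suicide attempt or suicide risk.

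State in F3.1 how a recorded reason qualifies, how disagreement between the interview, hospital records and clinician reports is settled, and that the classification is made without knowledge of study arm. G2.2 says that notes will be entered in the VA record, so the extract given to the classifier should have anything that reveals the arm removed.

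Report psychiatric admission for any reason as a descriptive health-services outcome.

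The cost is small. The sources are already in use and reasons are already recorded for psychiatric admissions. The added work is recording reasons for medical admissions and the masked classification step.
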